- **Sample Size.** In our pilot study of the effects of phlebotomy, we did not measure HgbA1C, but did perform glucose tolerance testing where the difference in area under the curve from pre- to post-treatment was  $1130 \pm 1970$  mg-min/dl. Assuming this average change would be maintained through the day, and converting this change to the relative change in HgbA1C, the change would be expected to be a decrease of ~0.6% (in A1C units, not a change of 0.6% magnitude). With the variance observed, this means a sample size of 32 patients in each group will provide 80% power to detect a difference between the beginning and final HgbA1C in either treatment group at  $p < 0.05$  when pre- and post-phlebotomy results are compared within subjects. This agrees with the published results from another group that did measure HgbA1C, wherein they achieved a significant change ( $p < 0.001$ ) with an N of 31, but a shorter observation period and much less reduction in ferritin. A larger sample size (60/group, 240 total in Aim 1, half diabetes and half prediabetes, with

120 each being randomized to control and phlebotomy) will be recruited to facilitate possible subgroup analysis (e.g. stratification by age, treatment, race, sex) and to allow an up to 20% dropout rate, which is significantly higher than the experience of previous similar studies at Wake Forest University, wherein the dropout rates were in the 12-15% range. (In our pilot study, there were no dropouts.) Thus, we will be theoretically powered to analyze each target ferritin group separately, although the initial analysis will pool the two treatment groups.

- **Multisite study.** This is a multisite study, coordinated by WFUHS, and equal numbers will be recruited at each site, 120 at WFUHS and 120 at UNC Chapel Hill. The Liver substudy will recruit 40 people and the Glucose Tolerance Mechanism substudy will recruit 48 people. The sub studies will be conducted only at Wake Forest Baptist Medical Center.

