## **Interventions and Interactions**

*The essential features of interventions and interactions used to generate data for the study should be described.*

- **Intervention:** Periodic (every 8 weeks) phlebotomy of 500 mL (one “Unit”) sufficient to reduce serum ferritin from the upper half of normal to the lowest 20% of normal (Males 20-40, Females 20-40 ng/ml) (35). In our pilot study, subjects reached similar ferritin levels with donation of  $3.4 \pm 0.5$  Units. In that case subjects donated one Unit per month and there were no adverse events; that interval has been increased in this study to 8 weeks to conform to current Red Cross practices.
- **Sham Phlebotomy:** As any other study, interventions are subject to placebo effects, and the same is true for phlebotomy. We are thus including a sham phlebotomy as described in the procedures, below.
- **Study Protocol.** The inclusion and exclusion criteria are listed in **3.A**. We are including arms to address prediabetes and diabetes separately because there is the possibility that the former will respond more robustly to therapy because they will not have had the disease long enough to develop a significant degree of insulin deficiency, a feature of T2DM that may be difficult to reverse in middle-aged or older adults. Our small pilot trial showed improvement in both groups, but 2/3 of those with prediabetes reverted to normal glucose tolerance, a surprisingly good result. For the reason of reversibility cited above, we are not including anyone on insulin; furthermore, anyone on insulin or other agents with the potential to cause hypoglycemia are also excluded because if their insulin sensitivity improves with iron reduction, as the Preliminary Data suggest, they could be more prone to hypoglycemia.

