- c. Visit 2 (7-14 days) (fasting) (~1 hr):** Report to the Clinical Research Unit (CRU) at University of North Carolina at Chapel Hill (UNC) or Wake Forest (WF) School of Medicine. Review Adverse Events (AE's). Measure outcome variables (weight, blood pressure; blood for, insulin, lipid panel, CMP (14), Ferritin) and the Ultrasound Fibroscan (WFBH site only). Subjects who complete Visit 2 will be compensated \$50 for their time.

*Randomization* (1:1) to control (sham phlebotomy) or phlebotomy groups with final target ferritin levels of 20-40 ng/ml for males and 20-40 for females. Phlebotomy will not be performed if hemoglobin is lower than 12.5 g/dL for women and 13.0 g/dL for men; in that case, subjects will undergo repeat hemoglobin measurement every 2 months. If the hemoglobin value increases above the threshold for phlebotomy at Visits 3 or 4, phlebotomy will be performed; otherwise, participants will have an “end of study” visit 1 at six months. If blood pressure declines by > 20 mm Hg systolic, or pulse increases by > 30 bpm upon standing, phlebotomy will not proceed.

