### **Glucose Mechanisms Substudy Outcome Measures**

Our primary endpoint will be an improvement in the FSIGTT DI, which is the best predictor of diabetes of the many indices arising from MinMod analysis of FSIGTT data (41). Secondary analyses will be the indices that directly quantify the two hallmarks and principal pathogenic factors in T2DM, namely insulin secretory capacity (AIRg) and insulin sensitivity (Si). As in Aim 2, and as in the pilot study on which this Aim is modeled, we will pool the diabetes and prediabetes groups for the primary analysis. This study is powered for that group analysis based on our preliminary data, although we will subanalyze by subgroups and with ferritin, AIRg, and Si as continuous variables to determine if there is evidence for an optimal ferritin target.

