### **Analytical Plan**

#### **Statistical Plan and Data Analysis.**

The primary analysis will be an analysis of covariance to compare the mean change in the primary endpoint for each aim (HgbA1C at 6 months after phlebotomy for Aim 1, serum ALT at 12 months after phlebotomy for Aim 2, and DI at 6 months after phlebotomy for Aim 3) between the iron depletion and control groups in the full cohort of patients after controlling for the baseline levels of those measurements. The baseline HgbA1C is included as a covariate to increase study power by accounting for regression to the mean between the two time points.

*Secondary Analyses.* The effects of iron depletion on secondary continuous outcomes will be evaluated using analysis of covariance with adjustment for the baseline level of the factor being analyzed as well as the baseline HgbA1C level. For example, we will determine the degree of response (e.g. change in average glucose by CGM) as a function of starting ferritin, ending ferritin, and change in ferritin for determination of dose-response relationships. Treatment effects on dichotomous outcomes (e.g., conversion of pre-diabetes to diabetes) will be evaluated by exact logistic regression, controlling again for the baseline level of the analyzed factor. Ordinal logistic regression will be applied to compare categorical variables with more than 2 ordered categories. In expanded models, interaction terms between the treatment assignment and baseline HgbA1C level will be added to evaluate if the treatment effect differs across the HgbA1C range, and, in particular, between the diabetic and pre-diabetic patients in the study.

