*Statistical Power.* In our pilot study of the effects of phlebotomy, we did not measure HgbA1C, but did perform glucose tolerance testing where the difference in area under the curve from pre- to post-treatment was  $1130 \pm 1970$  mg-min/dl. Assuming this average change would be maintained through the day, and converting this change to the relative change in HgbA1C, the change would be expected to be a decrease of  $\sim 0.6$ . With the variance observed, this means a sample size of 32 patients in each group will provide 80% power to detect a difference between the beginning and final HgbA1C in either treatment group at  $p < 0.05$  when pre- and post-phlebotomy results are compared within subjects. This agrees with the published results from another group using HgbA1C, wherein they achieved a significant change ( $p < 0.001$ ) with an N of 31, but a shorter observation period and much less reduction in ferritin (28). A larger sample size (60/group, diabetes and prediabetes, control and phlebotomy) will be recruited to facilitate possible subgroup analysis (e.g. stratification by age, treatment, race, sex) and to allow for dropout. (Previous studies requiring FSIGTT at WF, had dropout rates were in the 12-15% range; in our pilot study, there were none.) Thus, we will be theoretically powered to analyze each target ferritin group separately, although the initial analysis will pool the two treatment groups.

The N for the change in transaminase levels by the same criteria (Aim 2) is 13, and in DI (Aim 3) is 16. Because the natural history is for both glycemia and NAFLD/NASH to deteriorate over time, the comparison of the control group with the treated group should be even more robust.

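### Allocation is described only as 1:1, so the planned 60 per disease-by-arm cell is expected but not secured, and the pooled substudies neither balance nor adjust for disease group

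*Combined protocol and SAP*

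**What the plan says.** All references are to the combined protocol and SAP.

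- Interventions and Interactions, Visit 2 (Randomization), gives the allocation ratio and nothing more: "1:1) to control (sham phlebotomy) or phlebotomy groups with final target ferritin levels". No section names a stratification factor, a block scheme, a list holder or a concealment method. The word stratification appears only for possible subgroup analyses.
- The Statistical Power paragraph plans the cells: "A larger sample size (60/group, diabetes and prediabetes, control and phlebotomy) will be recruited". The Sample Size paragraph agrees ("60/group, 240 total in Aim 1, half diabetes and half prediabetes"), then adds "120 each being randomized to control and phlebotomy) will be recruited". It also sets 120 participants per site.
- The Study Protocol paragraph expects the two disease groups to behave differently: "We are including arms to address prediabetes and diabetes separately because" prediabetes may respond more strongly.
- The Glucose Mechanisms Substudy section, which says it follows Aim 2 in this, states "we will pool the diabetes and prediabetes groups for the primary analysis". The liver and glucose substudies have about 40 and 48 people, all at Wake Forest.
- The Statistical Plan compares arms on each aim's primary endpoint by ANCOVA "after controlling for the baseline levels of those measurements". For Aim 1 that baseline is HgbA1C. For Aims 2 and 3 it is ALT or DI, with no disease-group term. Baseline HgbA1C is added for secondary continuous outcomes but not for these two primary analyses.

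**The concern.** The plan treats disease group as important enough to set its cell sizes and to speak of separate arms. It then names no mechanism that would produce those cells. In the main trial that affects the disease-group contrasts. In the substudies the two groups are pooled, the samples are small, and the primary model contains nothing that would absorb a chance difference in disease mix between arms. If disease group predicts the change in ALT or DI beyond the baseline value, such a difference adds noise to the estimated phlebotomy effect. It would also leave a substudy result open to the challenge that the arms differed in disease mix.

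**Working it through.** **Inputs from the documents.** 240 in total, 120 with diabetes and 120 with prediabetes; 60 per cell; two sites of 120; substudies of 40 and 48; up to 20% dropout; AUC change 1130, SD 1970. **Assumptions, because the documents give no figure:** half of each substudy has diabetes; baseline–outcome correlation 0.5; a disease-group shift in outcome, given baseline, of 0, 0.5 or 0.8 SD.

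**1. The plan's own figure.** 4 × 60 = 240 = 2 × 120. The cells are consistent with the totals.

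**2. What a bare 1:1 ratio delivers in the main trial.**
- Simple allocation: a cell is Binomial(120, 0.5), SD √(120 × 0.25) = 5.5, 95% range 49–71. P(one disease group within 55–65) = 1 − 0.315 = 0.685, so P(at least one outside) = 1 − 0.685² = 53%.
- A list balanced only overall (120 per arm): hypergeometric, SD √(120 × 0.25 × 120/239) = 3.9, 95% range 52–68. A given cell is off by 5 or more with probability 24.5%.

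**3. Cost within a disease group.** Two-sample power after 20% dropout is Φ(1130 / [1970 √(1/n₁ + 1/n₂)] − 1.96):
- 60/60 (48/48 completing): 80.2%
- 52/68 (41.6/54.4): 79.5%
- 49/71 (39.2/56.8): 78.9%

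The loss is at most 1.3 points over these ranges.

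**4. Disease mix in the substudies.** Chance that the diabetes share differs between arms by 20 points or more:
- n=40: 34% with equal arms (hypergeometric; a 12:8 split of the 20 with diabetes, or worse); 27% under simple allocation (simulation).
- n=48: 15% with equal arms (the smallest reachable gap of at least 20 points is 15:9, or 25 points); 19% under simple allocation.

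**5. Effect on precision.** Set the within-group outcome SD to 1. The residual variance given baseline is 1 − 0.5² = 0.75. Leaving out an unbalanced half-and-half factor with shift δ adds δ²/4.
- δ = 0.5: 0.0625 / 0.75 = 8% more variance.
- δ = 0.8: 0.16 / 0.75 = 21% more variance.

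Simple allocation also makes arm sizes unequal, which costs 2–4% even when δ = 0. Simulated variance ratios, simple against stratified, agree: 1.10–1.13 at 0.5 SD and 1.22–1.25 at 0.8 SD, over both substudy sizes. With equal arms but no strata the inflation is 7–23% at n=40 and 9–20% at n=48.

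**6. Whether stratifying is enough.** At n=40 and δ = 0.8, the variances of the effect estimate are:
- Simple allocation, planned model: mean model-based variance 0.097.
- Stratified allocation, planned model: true variance about 0.077–0.078, but mean model-based variance 0.094. The gain hardly reaches the confidence interval.
- Simple allocation with a disease-group term: 0.082, most of the gain.

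Stratifying the trial by disease group and site alone does not balance a substudy either. With 20 of 60 people drawn from each Wake Forest disease stratum (30 per arm), the count with diabetes in one arm has variance 20 × 0.25 × 40/59 = 3.39. The gap in diabetes share then has SD √(2 × 3.39)/20 = 13 points, against 16 points under simple allocation.

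**The case against.** The strongest reply is that the plan is silent on method, not explicitly unstratified. The text about 120 each, and the reference to arms for prediabetes and diabetes, could mean that randomization is done within disease group. That stands. A reader might infer that the cells of 60 will not be delivered; the documents support only that nothing stated secures them. If stratification was intended, one sentence settles it.

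The second reply is that the documents do not show disease group shifting ALT or DI. That stands too. It is tempting to cite the pilot contrast in section 1.E (AUCg −10.3% in prediabetes, −2.9% in diabetes, p = 0.06). But that is a difference in response after phlebotomy, on another endpoint, in a pilot of 11 people. It suggests effect modification, not a shift common to both arms. Effect modification alone of 0.5 SD at n=40 inflates variance by only about 5% in simulation.

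Third, the Aim 1 model already contains baseline HgbA1C, the variable that largely defines the groups, and interaction and subgroup analyses are planned. This is why the Aim 1 effect is small. It does not help the Aim 2 and 3 primary models, which contain neither HgbA1C nor disease group.

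Finally, substudy enrolment is not always available as a stratum. Liver-substudy entry depends on ALT or liver stiffness plus viral serology. The metabolic panel and Fibroscan are first scheduled at Visit 2, the visit at which allocation occurs, and the serologies have no scheduled visit. This limits the remedy but not the point.

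**Conclusion.** The point holds as a modest design weakness that is cheap to remove. The planned cells of 60 are expected but unsecured. The effect on the Aim 1 primary is small: under 2 points of power even within a disease group, with baseline HgbA1C already in the model. The exposure lies in the two pooled substudies, where a gap of 20 points or more in disease mix has roughly a one-in-seven to one-in-three chance, assuming half of each substudy has diabetes.

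The consequence is lost precision. A reader might infer that the substudy estimates are biased, but chance imbalance under randomization is not systematic bias. The size of the loss rests on an assumption: a few percent of variance if disease group does not shift the outcome given baseline, and about 10–25% if it shifts it by 0.5–0.8 SD with a baseline correlation of 0.5. The documents cannot say which applies.

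**What to change.** 1. In the Visit 2 randomization paragraph, state that the Data Coordinating Center allocates centrally and with concealment, 1:1 in permuted blocks of varying size, stratified by disease group and site. With 60 enrolled per disease-by-site stratum, each splits 30/30 apart from an incomplete last block, and the cells of 60 follow.
2. State which stratum takes the undiagnosed HgbA1C 6.5–6.9% class listed in the inclusion criteria.
3. In the Statistical Plan, add disease group to the primary ANCOVA for every aim, and site for Aim 1. This lets the standard errors reflect the balance and protects the pooled substudies without relying on substudy strata.
4. Stratify by substudy enrolment only where membership is confirmed before allocation.

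The cost is a few sentences, a few more allocation lists and one or two model degrees of freedom, with no extra participants, visits or tests. Blocks may be partly predictable to unmasked procedure staff; varying the block size limits this. The 120/120 disease and site totals still depend on recruitment quotas, which stratification does not supply.

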*Phlebotomy:* Both groups will have a sleep mask-style blindfold placed or a barrier (e.g. a towel) will be placed between all subjects and the phlebotomy bag in order to prevent the subject from knowing if blood was drawn, and have a phlebotomy needle placed, usually in an antecubital vein. The treatment group will have 1 Unit (~500 mL) of blood removed, while in the placebo group the needle will remain clamped. After the usual 8-10 minutes required for removal of the unit, both groups will have the needle removed, be given a zero-calorie rehydration drink (12 oz) and remain seated for at least 5 min or until comfortable to stand. A snack will be offered. Blood pressure will be monitored after the procedure and if there is hypotension by the above criteria (see *Randomization*), the subject will be asked to remain another 5-10 min and encouraged to finish the drink or have a second. The phlebotomies or sham phlebotomies will be performed by research nurses in the CRU, who have the training and support to respond to a medical emergency. For considerations related to phlebotomy safety and the use of the placebo group, please refer Visit 3. *WFBH participants only:* The discarded phlebotomy blood will be de-identified and will be picked up by a representative from the [name], the sample will be stored in the Olin Physical Lab on the Reynolda campus, room 216. The blood will be used for in vitro experiments aiming to prevent thrombosis in extracorporeal circulation devices. An Institutional Review Board (IRB) must also approve any future research study using your blood sample.

*Review of laboratory findings:* Ferritin results will not be routinely available prior to phlebotomy, but will be reviewed 1-3 days after the visit. Once the serum ferritin results reach the target range (20-40 ng/ml), the subject will be moved to the End of Study sequence.

- **d. Visit 3 (8 weeks after Visit 2) (not fasting) (~1 hr.):** Review AE's. Draw blood for ferritin and perform on site determination of hemoglobin. If hemoglobin is lower than 12.5 g/dL for women and 13.0 g/dL for men, phlebotomy will not be performed and subject will be scheduled 8 weeks out for Visit 4. If the serum ferritin results from this visit have reached the target range (20-40 ng/ml), the subject will be moved to the End of Study sequence. If not, the subject will continue to Visit 4. Subjects who complete Visit 3 will be compensated \$50 for their time.

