- **e. Visit 4 (not fasting):** Review AE's. Draw blood for ferritin and perform on site determination of hemoglobin. If hemoglobin is lower than 12.5 g/dL for women and 13.0 g/dL for men, phlebotomy will not be performed and subject will be scheduled 8 weeks out for Visit 5. At this visit, after the sham phlebotomy, all of the Placebo Group will be scheduled to the “end of study” sequence. Three phlebotomies were the average needed for the treatment group in the pilot study to achieve goal ferritin. If serum ferritin results of the treatment group subjects from this visit have reached the target range (20-40 ng/ml), the subject will be moved to the End of Study sequence. If not, the subject will continue to Visit 5. Subjects who complete Visit 4 will be compensated \$50 for their time.
- **f. Visits 5-6, if needed (not fasting):** Hemoglobin and Ferritin will be drawn. If hemoglobin is lower than 12.5 g/dL for women and 13.0 g/dL for men, phlebotomy will not be performed and subject will be scheduled 6 months out to start the End of Study sequence. If the serum ferritin results from Visit 5 have reached the target range (20-40 ng/ml), the subject will be moved to the End of Study sequence. If not, the subject will continue to Visit 6. After Visit 6, all subjects, regardless of serum ferritin results, will move to the End of Study sequence. Subjects who complete these visits will be compensated \$50 for their time per visit.
- **g. End of Study Visit 1 (6 months ± 2 weeks after last phlebotomy visit) (fasting) (~1 hr.):** Patient should come in fasting. Review AE's. Perform outcome measures (blood pressure, weight, CMP (14), CBC platelets no diff., insulin, HgbA1C, CRP, lipid panel, ferritin. Fibroscan (WFBH site only), place CGM, which the subject will mail back in a prepaid mailer. Subjects who complete this visit will be compensated \$100 for their time.

- **h. End of Study Visit 2 (6 months  $\pm$  2 weeks after E.O.S. 2) (fasting) (~1 hr.):** Patient should come in fasting. Review AE's. Perform outcome measures (CGM placement, blood pressure, weight, CMP (14), CBC platelets no diff., insulin, lipid panel, HgbA1C, ferritin, CRP, Fibroscan (WFBH site only)). Place CGM, which the subject will mail back in a prepaid mailer. Subjects who complete this visit will be compensated \$100 for their time.

- Study procedure: Liver Substudy
- The Screening Visit and Visit 1 will be the same as the Basic Study

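### The phlebotomy stop rule is a two-sided ferritin range, so read literally a result below 20 ng/mL leads to another phlebotomy visit

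*Combined protocol and SAP*

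**What the plan says.** Randomization assigns the treated group to phlebotomy "with final target ferritin levels of 20-40 ng/ml for males and 20-40 for females". Under Study Procedures, Review of laboratory findings, the rule for ending phlebotomy is "Once the serum ferritin results reach the target range (20-40 ng/ml), the subject will be moved to the End of Study sequence". The same paragraph gives the timing: "Ferritin results will not be routinely available prior to phlebotomy, but will be reviewed 1-3 days after the visit".

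The visit descriptions repeat the 20-40 trigger and then give the alternative:

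- Visit 3: "If not, the subject will continue to Visit 4".
- Visit 4, treated group: "If not, the subject will continue to Visit 5".
- Visit 5: "If not, the subject will continue to Visit 6".

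The series is capped: "After Visit 6, all subjects, regardless of serum ferritin results, will move to the End of Study sequence". Draws are also withheld when hemoglobin is below 12.5 g/dL (women) or 13.0 g/dL (men), or when the standing blood pressure or pulse check fails. Visits are 8 weeks apart. No sentence sets a ferritin floor or says what to do with a result below 20.

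**The concern.** A result of 15 ng/mL is not in the range 20-40. Taken at its word, the rule treats it like a result of 60 and brings the participant back for another unit, which moves them further from the target. The existing brakes look at hemoglobin, blood pressure, pulse and visit count, but not at ferritin, so a participant already under the protocol's own lower limit could be bled again. The protocol has a reason of its own to avoid this: section 1.E reports a hint from the pilot that going down to the very bottom of normal was not the most beneficial level.

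**Working it through.** **1. What each result triggers at Visits 3, 4 and 5 (treated group, literal reading).**

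- Above 40: continue to the next phlebotomy visit.
- 20 to 40: move to End of Study.
- Below 20: outside the stated range, so the 'if not' branch applies and the participant continues.

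**2. Further units permitted.** Draws can occur at Visits 2 to 6, five in all. The result is known only 1-3 days after the visit, so that visit's own unit has already been taken. Counting later draws only:

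- First result below 20 at Visit 3: draws at Visits 4, 5 and 6, up to 3 more.
- At Visit 4: draws at Visits 5 and 6, up to 2 more.
- At Visit 5: a draw at Visit 6, up to 1 more.

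These are maxima. Low hemoglobin at Visit 5 sends the participant to End of Study. A draw blocked at Visit 3 or 4 could let ferritin recover into 20-40, which ends phlebotomy under the same literal rule.

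**3. Pilot inputs (section 1.E).** Men, 9 of 11, started at 219 and fell by 150. Women, 2 of 11, started at 92 and fell by 56. The average was 3.4 units. The stated volume reproduces: 3.4 × 0.5 L = 1.7 L. Implied mean end values:

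- Men: 219 − 150 = 69 ng/mL.
- Women: 92 − 56 = 36 ng/mL.
- All 11: (9 × 69 + 2 × 36)/11 = 63 ng/mL.

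**4. Mean proportional fall per unit.** Units are not given by sex, so the pooled 3.4 is assumed for each.

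- Men: (69/219)^(1/3.4) = 0.712.
- Women: (36/92)^(1/3.4) = 0.759.

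**5. Would the range be skipped?** If the previous reading was just above 40, the next is about 40 × 0.712 = 28.5 in men or 40 × 0.759 = 30.4 in women. Both lie inside 20-40. Going from above 40 to below 20 between consecutive readings needs a factor below 20/40 = 0.5, that is, a fall of more than half and more than 20 ng/mL. The mean factors are well short of that. The protocol gives no distribution of individual falls per unit, so the proportion of people who would fall that fast cannot be calculated.

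**6. Side calculation: units for a man starting at 219 to reach 40**, on the same 3.4-unit assumption.

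- Proportional fall: ln(40/219)/ln(0.712) = 5.0 units.
- Constant fall: 150/3.4 = 44.1 ng/mL per unit, so (219 − 40)/44.1 = 4.1 units.

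**The case against.** The best defence is intent. Objectives and Intervention both describe bleeding enough to bring ferritin down from the upper half of normal into the lowest fifth. The later visits are labelled as held only if needed. Someone who comes down from above 100 to 15 has, in ordinary speech, reached the target and needs no further unit. That is a fair reading and probably the intended one. It does not remove the gap, because staff at two sites apply the visit text, and that text pairs a two-sided range with an unqualified alternative.

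The second defence is that the hemoglobin and orthostatic checks, the 8-week spacing and the five-draw cap limit harm. They do. They limit the consequence without stopping the wrong action.

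Two stronger readings are tempting, and the documents support neither.

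- A reader might note that pilot men lost about 44 ng/mL per unit on average, more than twice the width of the range, and infer that many men would step over it. That applies a constant fall, taken from men averaging 219, to much lower values. A man starting at 101 would be at 101 − 3 × 44.1 = about −31 at Visit 5, which is impossible. Section 1.E itself ties a lower start to a smaller absolute fall.
- A reader might take the wide spread of post-treatment ferritin in Table 1 as a rate of undershoot for this trial. Those patients started at a mean of 398 and were bled to an aim of 50, with no draw interval or stopping rule stated. The table says nothing about the rate here.

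**Conclusion.** The gap in the wording is certain. Its practical size is bounded at 3, 2 or 1 further units, according to whether the first result below 20 comes at Visit 3, 4 or 5. The frequency is unknown: not expected at the pilot's mean proportional fall, possible for individuals with larger falls. That statement rests on applying the pooled 3.4 units to each sex and on monthly or faster pilot draws carrying over to 8-week spacing. The comparison with sham is not biased by this, and type I error and power are not touched. It is a minor safety point.

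A side note concerns the background text. Intervention says pilot participants reached ferritin levels similar to 20-40, but the implied mean in men is about 69; the women's 36 fits. A reader might go further and infer that the sentence "Three phlebotomies were the average needed for the treatment group in the pilot study to achieve goal ferritin" is wrong. That cannot be shown, because the pilot's goal is not given. Nor does the men's mean show that no man reached 20-40. A man starting at 219 would need about 4 units (constant fall) to 5 units (proportional fall). None of this changes what the trial does.

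**What to change.** In Study Procedures, under Review of laboratory findings, Visit 3, Visit 4 and Visits 5-6, replace the trigger about reaching the 20-40 range with: *serum ferritin is 40 ng/mL or lower*. Then add: *No further unit is drawn after any such reading, including one below 20.* The 20-40 range can stay elsewhere as the description of the target.

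The change does not prevent the unit taken at the visit that yields the reading, because the result comes afterwards. It prevents every later one.

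The cost is a short wording amendment and a note to both sites. There is no extra sample, visit or participant, and the sham schedule is unchanged. When making it, the sponsor could check the actual pilot end values and adjust the comparison in Intervention; that is optional.
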